7.1.6. Sensitivity and Supportive Analyses

To assess the robustness of the primary efficacy results, the primary efficacy analyses will be repeated using following sensitivity and supplementary approaches:

- **ESA Users with Hgb rapid increase at Week 2**; the primary efficacy analysis will be repeated for the ITT population excluding the ESA users whose daprodustat dose level was decreased by one step at Week 2.
- **Efficacy ND Population**; the primary efficacy analyses will be repeated for the Efficacy ND population (see Section 4).
- **mITT/PP Population**; the primary efficacy analyses will be repeated for the mITT and PP populations as the supplementary analysis.
- **Evaluable Hgb**; if there are Hgb values considered to be impacted by a red blood cell transfusion, a whole blood transfusion or marketed rhEPO/ESAs, supplementary analysis excluding the Hgb values from the analyses of primary endpoint will be conducted.
- **Analysis of covariance (ANCOVA)**; it will be conducted as supplementary analysis to MMRM. This model includes treatment group, baseline Hgb, and prior ESA use. The analysis population will be the mITT population and the analysis will be repeated in the PP population.
- **Tipping point analysis**; based on multiple imputation it will be conducted as sensitivity and supplementary analysis to missing data assumption. This analysis explores points where non-inferiority is not confirmed (tipping points) by changing assumption to missing data and repeating imputations. The analysis population will be ITT population and the analysis will be repeated in the mITT and PP populations.

7.1.6.1. Evaluable Hgb

The analyses will be based on the ITT population, unless otherwise specified. In a strategy for intercurrent event of a red blood cell transfusion, a whole blood transfusion and commercial ESA medication, the following hypothetical scenario is considered to assess what would have happened if the event did not occur. Non-evaluable Hgb (described in 15.6.3), which is caused by this event, will be treated as missing, and will be analyzed based on missing at random assumption (the observations of missing depend on just observed values, not on unobserved values).

Model Specification

 • Evaluable Hgb defined in Section 15.6.3 will be used for the analysis. Non-evaluable Hgb will be treated as missing. • Analyses will be conducted by MMRM. See Section 7.1.5.1 for the detail.
Model Results Presentation

 • The point estimates of adjusted mean Hgb during the primary efficacy evaluation period for each treatment will be presented with the associated standard errors and 95% CIs. The treatment difference, standard error, its 95% CI, and the non-inferiority p-value (described in Section 7.1.5.1, Model Specification) will also be presented.

7.1.6.2. Analysis of Covariance (ANCOVA)

The analyses will be based on the mITT and PP populations, unless otherwise specified. In a strategy for intercurrent event of study withdrawal, a subject who has the event before Week 40 will not be included in analyses. If a subject has the event on or after Week 40, the event is taken to be irrelevant to the mean Hgb during primary efficacy evaluation period (i.e., observed values will be used for the analysis).

Model Specification

- A subject must have at least one Hgb measurement during the primary efficacy evaluation period (Week 40 to Week 52) to be included in this analysis.
- Analyses will be conducted by an ANCOVA model as follows:

$$\text{mean}(\text{Hgb}_i) = \beta_0 + \beta_{\text{baseline}} * \text{Baseline}_i + \beta_j + \beta_l + \varepsilon$$

$$\text{mean}(\text{Hgb}_i) = (\text{Hgb}_{i,\text{Week 40}} + \text{Hgb}_{i,\text{Week 44}} + \text{Hgb}_{i,\text{Week 48}} + \text{Hgb}_{i,\text{Week 52}})/4:$$

mean Hgb during the primary efficacy evaluation period for subject i

β_0 : Intercept

β_{baseline} : baseline Hgb effect

Baseline_i: Hgb measurement for subject i

β_j : treatment effect (j= daprodustat, epoetin beta pegol)

β_l : prior ESA use effect (l = ESA user, ESA non user)

ε : random error

i: subject (i = 1, 2, ..., N)

N: number of subjects included in the analysis

- LS means for treatment j will be calculated as follows:

$$\mu_j = \beta_0 + \beta_{\text{baseline}} * \mu_{\text{baseline}} + \beta_j + (\beta_{\text{ESA user}} + \beta_{\text{ESA non-user}})/2$$

μ_j : LS mean for treatment j

μ_{baseline} : mean for baseline Hgb

- The treatment difference for mean Hgb during the primary efficacy evaluation period will be calculated as follows:

$$\mu_{\text{daprodustat}} - \mu_{\text{epoetin}} = \beta_{\text{daprodustat}} - \beta_{\text{epoetin}}$$

- P-value for non-inferiority test will be based on the following *t* test statistic (Mascha 2011):

$$t = (\mu_{\text{daprodustat}} - \mu_{\text{epoetin}} - \delta)/s$$

δ : non-inferiority margin (= -1.0 g/dL)

s: standard error of treatment difference

The non-inferiority p-value is the probability of observing a larger value of *t* in a *t* distribution with degrees of freedom of residual.

Model Checking & Diagnostics

- Not applicable

Model Results Presentation

- The point estimates of adjusted mean Hgb for each treatment will be presented with the associated standard errors and 95% CIs. The treatment difference, standard error, its 95% CI, and the non-inferiority p-value (described in Section 7.1.5.1, Model Specification) will also be presented.

Subgroup Analyses

- The subgroup analyses will be based on the modified ITT population.
- The same statistical analysis method (using ANCOVA described as above) will be applied to estimate the mean Hgb during the primary efficacy evaluation period for each subgroup.
- Graphical summaries for the treatment differences of the mean Hgb during the primary efficacy evaluation period and the associated 95% CIs will be produced using a forest plot

7.1.6.3. Tipping Point Analysis

The analyses will be based on the ITT population, unless otherwise specified.

Tipping point sensitivity analyses will be conducted under a range of missing data assumptions to determine how extreme assumptions need to be for non-inferiority conclusions to change. Assumptions about missing Hgb values on the daprodustat and epoetin beta pegol arm will vary independently, and will include scenarios where subjects with missing data on daprodustat have worse outcomes than subjects with missing data on epoetin beta pegol. If the tipping point scenario is clinically plausible, the conclusion under missing at random may be questionable.

In a strategy for intercurrent event of study withdrawal, a hypothetical scenario is considered to assess what would have happened if the event did not occur. For this hypothesis, the missing data due to this event would occur at not-at-random manner, that is the observations of missing depend on unobserved values, which will be mimicked with delta-adjustment analysis in this study.

Model Specification

- A tipping point is the critical point that reverses the study conclusion (i.e., non-inferiority test).
- Tipping point analysis for this study takes following steps:
 1. multiple imputation
 2. delta adjustment
 3. analyses for each imputed complete dataset.
 4. making combined results

As a reference, programming codes for tipping point analysis are described by Yuan 2014 as %midata macro in the appendix.

1. Multiple Imputation Strategy

- Imputations will be conducted by a multiple imputation method using the SAS PROC MI procedure.

- The number of imputations will be set to 200.
 - The seed for reproducibility is set to 201753.
 - The analysis will not include subjects who are in the ITT population but who don't have any Hgb measurement on and after Week 4 (i.e., withdrawn at Week 2).
 - Initially, to obtain a monotone missing dataset from a non-monotone missing dataset, the imputation for intermittent missing values will be done using MCMC by treatment.
 - After obtaining the dataset with only the monotone missing patterns, imputation based on MAR assumption can be performed by treatment in a sequential manner. Assume that repeated measures variables Y_i ($i=1, \dots, n$) are included in the imputation model (linear regression model with a covariate of baseline Hgb). The Y_1 is imputed first based on the covariate. Then Y_2 would be imputed using the covariate and Y_1 and so on for each variable until Y_n is imputed using the covariates and Y_1, \dots, Y_{n-1} .
2. Delta (Δ) Adjustment Strategy
- Based on MAR assumption ($\Delta=0$), monotone missing data that occurred before Week 52 will be imputed as shown above. To mimic missing not at random manner, sequentially increasing Δ will be added to imputed values where Δ represents a change in Hgb over 4-week interval. No Δ adjustments will be done for intermittent missing values.
 - Sequentially increasing Δ adjustment is to add $n \cdot \Delta$ value on the imputed value of n th monotone missing data. The longer the period of time with monotone missing, the larger Δ value will be added. Suppose a subject who has withdrawn at Week 40 visit, in other words, this subject has monotone missing data from Week 44 to Week 52. Imputations are conducted on missing data of Week 44, 48, and 52 and then Δ is added to an imputed value on Week 44, 2Δ on Week 48, and 3Δ on Week 52.
 - Initially, the Δ values will be explored for both arms and will range from -4.0 to 4.0 g/dL with a 1.0 g/dL increment. Once the "rough" tipping point is found with the larger increment ($=1.0$ g/dL), the exploration will be done with smaller increments to find the more precise tipping points. In order to keep clinically plausible range, if delta adjusted imputed value is lower than 7.0 g/dL or higher than 14.0 g/dL then the value will be replaced by 7.0 g/dL or 14.0 g/dL respectively. To reduce computationally intensive iterations, the further worsening scenarios beyond a range from -4.0 to 4.0 g/dL will not be examined.
3. Analysis Strategy for Each Imputed Complete Dataset
- The analysis using a MMRM (described in Section 7.1.5.1) will be applied and will be repeated for each imputed complete dataset. The calculation of the denominator degrees of freedom may be simplified (e.g., between-within degrees of freedom) for the imputed complete dataset. The mean differences between the mean Hgb during the primary efficacy evaluation period will be estimated for each imputed complete dataset.
4. Combine results of m datasets
- For each pair of deltas (one independently assigned delta for each treatment arm), Rubin's rules (Rubin 1987) will be used to combine results of all imputed datasets, using SAS PROC MIANALYZE procedure. As a result, for each pair of delta values, a single estimated treatment difference and its standard error will be produced, with which a one-sided non-inferiority p-value can be calculated using non-adjusted degree of freedom.

Model Checking & Diagnostics

- For the model checking & diagnostics of MMRM analyses, see the Section 7.1.5.1.

Model Results Presentation

 Graphics depicting treatment difference and non-inferiority p-value surfaces will be produced using an enhanced tipping point approach (Liublinska 2014); A colored heat map that illustrates the gradual change of non-inferiority p-values will be produced. 
 In a display, colored grids highlight delta combinations that result in rejecting the null hypothesis (i.e., non-inferiority established).
Sensitivity and Supplementary Analyses

 The analysis will be repeated for mITT and PP population.

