4. ANALYSIS POPULATIONS

Population	Definition / Criteria	Analyses Evaluated
All Screening	
 Consists of all subjects who are given subject number and whose data are collected, including demographics at screening 	
 Study Population
Enrolled	
 Consists of subjects in All Screening except for screen failures (who never passed screening even if rescreened). 	
 Study Population (some displays for EudraCT)
Randomized	
 Consists of all subjects who are given randomization number regardless of whether they actually receive study treatment. 	
 Study Population
Safety	
 Consists of all subjects who receive at least one dose of study treatment. Subjects will be analyzed according to the treatment received.^[1] This population will be used for safety analyses. 	
 Study Population Safety
Efficacy Non-dialysis (Efficacy ND)	
 Consists of Cohort 1 subjects (both ESA users and ESA non-users) and Cohort 3 subjects (both ESA users and ESA non-users) who are given randomization number with Hgb measurement at both baseline and at least one scheduled visits following the baseline. Subjects will be analyzed according to randomized treatment. 	
 Study Population Efficacy
Efficacy Peritoneal Dialysis (Efficacy PD)	
 Consists of Cohort 2 subjects who are given randomization number with Hgb measurement at both baseline and at least one scheduled visits following the baseline. 	
 Study Population Efficacy
Intent-To-Treat (ITT)	
 Consists of Cohort 1 subjects (only ESA users) and Cohort 3 subjects (both ESA users and ESA non-users) who are given randomization number with Hgb measurement at both baseline and at least one scheduled visits following the baseline. 	
 Study Population Efficacy

[figure not shown]
Population	Definition / Criteria	Analyses Evaluated
	
 Subjects will be analyzed according to randomized treatment. This population will be the primary population for an assessment of non-inferiority. 	

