7.1.4. Strategy for Intercurrent (Post-Randomization) Events

Intercurrent events	Strategy
Study withdrawal	The following hypothetical scenario is considered; what would have happened if the event did not occur. The primary analyses using MMRM assume missing at random mechanism, that is the observations of missing depend on just observed values, not on unobserved values.
Prohibited medications (except for commercial ESA medications)	Basically, the occurrence of the event is taken to be irrelevant. Subjects with long-term use of prohibited medications will be excluded from the PP population.
Blood transfusion and/or commercial ESA medication	In primary analyses, the occurrence of the event is taken to be irrelevant.
Intermittent missing	The following hypothetical scenario is considered to assess what would have happened; if the event did not occur. The hypothesis is that an intermittent missing would occur at at-random manner, that is the observations of the missing depend on just observed values, not on unobserved values.

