7.1.5.1. Statistical Methodology Specification

Endpoint / Variables

 • Mean Hgb during the primary efficacy evaluation period (Weeks 40 to 52)
Model Specification

 • Analyses will be conducted by MMRM as follows: $Hgb_{ik} = \beta_0 + \beta_{baseline} * Baseline_i + \beta_j + \beta_k + \beta_{jk} + \beta_{baseline*k} * Baseline_i + \epsilon_{ik}$ 
Hgb_{i, week}: Hgb measurement for subject i at visit k β_0: Intercept $\beta_{baseline}$: baseline Hgb effect Baseline_i: Hgb measurement for subject i β_j: treatment effect (j= daprodustat, epoetin beta pegol) β_k: visit effect (k = Week 4, Week 8, ..., Week 52) β_{jk}: treatment-by-visit interaction $\beta_{baseline*k}$: baseline-by-visit interaction ϵ_{ik}: random error for subject i at visit k i: subject (i = 1, 2, ..., N) N: number of subjects included in the analysis
 • The model parameters will be estimated using Restricted Maximum Likelihood (method=REML) with the Newton-Raphson algorithm. • The Kenward-Roger method for calculating the denominator degree of freedom will be used. • The variance-covariance structures for repeated measures within the individual subject will be unstructured (type=UN). • LS means for treatment j at visit k will be calculated as follows. $\mu_{jk} = \beta_0 + \beta_{baseline} * \mu_{baseline} + \beta_j + \beta_k + \beta_{jk} + \beta_{baseline*k} * \mu_{baseline}$ 
μ_{jk}: LS mean for treatment j at visit k $\mu_{baseline}$: mean for baseline Hgb
 • Model based mean Hgb during the primary efficacy evaluation period for treatment j will be calculated as follows $\begin{aligned} \mu_j^{*evaluation} &= (\mu_j^{*Week\ 40} + \mu_j^{*Week\ 44} + \mu_j^{*Week\ 48} + \mu_j^{*Week\ 52})/4 \\ &= \beta_0 + \beta_{baseline} * \mu_{baseline} + \beta_j + (\beta_{Week\ 40} + \beta_{Week\ 44} + \beta_{Week\ 48} + \beta_{Week\ 52})/4 + (\beta_j^{*Week\ 40} + \beta_j^{*Week\ 44} + \beta_j^{*Week\ 48} + \beta_j^{*Week\ 52})/4 + (\beta_{baseline*Week\ 40} + \beta_{baseline*Week\ 44} + \beta_{baseline*Week\ 48} + \beta_{baseline*Week\ 52}) * \mu_{baseline}/4 \end{aligned}$ • The treatment difference for model based mean Hgb during the primary efficacy evaluation period will be calculated as follows $\begin{aligned} \mu_{daprodustat}^{*evaluation} - \mu_{epoetin}^{*evaluation} &= \beta_{daprodustat} - \beta_{epoetin} + (\beta_{daprodustat*Week\ 40} + \beta_{daprodustat*Week\ 44} + \beta_{daprodustat*Week\ 48} + \beta_{daprodustat*Week\ 52})/4 - (\beta_{epoetin*Week\ 40} + \beta_{epoetin*Week\ 44} + \beta_{epoetin*Week\ 48} + \beta_{epoetin*Week\ 52})/4 \end{aligned}$ • P-value for non-inferiority test will be based on the following t test statistic (Mascha 2011):

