15.3.1. Definitions of Assessment Windows for Analyses

Analysis Time Point	Definitions
Screening ^[1]	Data collected in Screening visit If multiple records are present, the latest record will be used for analysis.
Day 1 ^[1]	Data collected in Day 1 visit If multiple records are present, the latest record will be used for analysis.
Week 2	Data collected in Week 2 visit ^[2]
Week 4	Data collected in Week 4 visit
Week 8	Data collected in Week 8 visit
Week 12	Data collected in Week 12 visit
Week 16	Data collected in Week 16 visit
Week 20	Data collected in Week 20 visit
Week 24	Data collected in Week 24 visit
Week 28	Data collected in Week 28 visit
Week 32	Data collected in Week 32 visit
Week 36	Data collected in Week 36 visit
Week 40	Data collected in Week 40 visit
Week 44	Data collected in Week 44 visit
Week 48	Data collected in Week 48 visit
Week 52	Data collected in Week 52 visit
Follow-up	Data collected in Follow-up visit

Note:

Any unscheduled visit will not be slotted to a particular time point.

[1] For rescreened subjects, data collected in screening-pass visit (i.e. screening and day 1 visit where the subject has passed a screening test) will be used for analysis. They may have multiple records at Screening and/or Day 1 visit, which associates with a screening pass visit and screening failure visit(s) (see Section [15.6.1](#) and Section [15.6.2](#))

[2] Only ND subjects randomized to Cohort 3

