16. REVISION HISTORY

Note that minor wording changes are not included in below.

Reporting and Analysis Plan_201753_Amendment 1 [19-NOV-2018]		
Section # and Name	Description of Change	Brief Rationale
Cover page	Approvers were changed.	Changed according to INS_689064 (1.0)
5.4.2 Examination of Subgroups	Cutoff values of baseline Hgb for ESA non-users and ERI were changed.	Cutoff value of baseline Hgb is aligned with stratification factor in randomization. Cutoff value of ERI was reconsidered.
6.1 Overview of Planned Study Population Analyses 15.10.4 Table of Contents for SAC Deliverable	Listing of Other Baseline Characteristics including prior ESA type, standardized prior ESA dose, ERI, iron use, diabetes, and CKD stage was added.	Required information was added.
6.2 Planned Summary Display Details 15.6.2 Study Population	Added the period of time on dialysis for PD subjects in demographic characteristics.	PD subjects are on peritoneal dialysis.
6.2 Planned Summary Display Details	Added compliance up to week 2 and week 2 to 4 for only cohort 3	Subjects in cohort 3 have week 2 visit.
7.1 Primary Efficacy Analyses 15.10.4 Table of Contents for SAC Deliverable	Added tables of the tipping point analysis	It would facilitate review of tipping point results.
7.1.6.1 Evaluable Hgb	Blood transfusion impacting Hgb values was clarified as red blood cell transfusion and whole blood transfusion.	Clarification
7.1.6.3 Tipping Point Analysis	Added statement of subjects who do not have Hgb on and after week 4 will be excluded in the tipping point analysis	The subjects are not included in the primary analysis.
7.1.6.3 Tipping Point Analysis	The number of imputations was reconsidered and a text was updated.	Modifications
7.2 Principal Secondary Efficacy Analyses	A method to construct 95% CI and one-sided p-value for odds ratio has been specified in Section 7.2.5.1 Statistical Methodology Specification	Clarification
7.2.5.1 Statistical Methodology Specification	Added handling to a problem with quasi-complete separation.	The problem with quasi-complete separation may occur.

CONFIDENTIAL

201753

Reporting and Analysis Plan_201753_Amendment 1 [19-NOV-2018]		
Section # and Name	Description of Change	Brief Rationale
7.3.1 Endpoint / Variables	Subgroup analyses by baseline Hgb for Hgb raw value, change from baseline in Hgb, number of subjects with Hgb within target range were added.	Analyses required from PMDA consultation

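### The ITT tipping point analysis leaves out ITT subjects with no Hgb from Week 4 on, although its own imputation model could include them; this can overstate robustness, by an amount that depends on how many there are

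*SAP*

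**What the plan says.** SAP Section 7.1.6 gives the purpose: "This analysis explores points where non-inferiority is not confirmed (tipping points) by changing assumption to missing data and repeating imputations". Section 7.1.6.3 bases the analysis on the ITT population unless otherwise specified, and then specifies otherwise: "The analysis will not include subjects who are in the ITT population but who don't have any Hgb measurement on and after Week 4", which it glosses as withdrawal at Week 2. The revision history (Section 16) gives the reason: "The subjects are not included in the primary analysis".

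Five other places bear on this:

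- Section 4 admits to ITT any eligible randomized subject "with Hgb measurement at both baseline and at least one scheduled visits following the baseline".
- Section 15.3.1 limits the Week 2 visit: "Only ND subjects randomized to Cohort 3".
- Section 7.1.5.1 defines the MMRM visits: "visit effect (k = Week 4, Week 8, ..., Week 52".
- Section 7.1.4 gives the primary missing-data assumption: "The primary analyses using MMRM assume missing at random mechanism".
- In the sequential imputation of Section 7.1.6.3, the first variable "is imputed first based on the covariate", the covariate being baseline Hgb. The nth monotone missing visit then receives n times delta, and adjusted values are held between 7.0 and 14.0 g/dL.

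**The concern.** The stated reason describes a limit of the observed-data MMRM, and that limit disappears after imputation. Every ITT subject has a baseline Hgb. A subject with nothing from Week 4 on has a purely monotone gap, which the plan's model can fill by arm. The MMRM is then fitted to completed data sets in which that subject would have Weeks 4 to 52. Nothing technical forces the exclusion.

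No other analysis covers these subjects under a missing-not-at-random assumption. The primary and evaluable-Hgb analyses assume missing at random. The ANCOVA needs Week 40-52 data, as do the mITT and PP repeats of the tipping point analysis. The trial is open-label, so early withdrawal that differs by arm cannot be ruled out. The one analysis meant to stress missing outcomes therefore omits the subjects who miss every modelled visit. The ITT logistic regression (Section 7.2.5.1, Table 2.26) keeps them as non-responders, so two displays labelled ITT would rest on different sets.

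**Working it through.** The plan gives no SD, dropout rate or count of affected subjects, so there is no stated figure to reproduce.

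**Inputs from the plan.** About 286 ND subjects randomized 1:1 (Section 2.3), so 286/2 = 143 per arm; margin -1.0 g/dL (Section 7.1.5.1); delta grid -4.0 to 4.0 and limits 7.0 and 14.0 g/dL (Section 7.1.6.3).

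**Assumptions.** Mean 12.0 g/dL in both arms, true difference 0, k affected subjects per arm.

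**Deltas carried.** With Week 4 as the first missing visit, Weeks 40, 44, 48 and 52 are the 10th to 13th, so these subjects would carry 10 to 13 deltas.

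**Largest shift in the difference.** Daprodustat to the floor: k x (7.0 - 12.0)/143. With the same number of epoetin subjects at the ceiling: k x (-5.0 - 2.0)/143.

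| k per arm | daprodustat only | both arms |
|---|---|---|
| 1 | -0.035 | -0.049 |
| 2 | -0.070 | -0.098 |
| 3 | -0.105 | -0.147 |
| 5 | -0.175 | -0.245 |

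With 130 per arm, one subject gives -5/130 = -0.038, or -7/130 = -0.054 paired.

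**Whether the grid tips.** Take the worst corner: all missing daprodustat values at 7.0, all missing epoetin values at 14.0, and an assumed SD of 0.7. With p = missing/N, the difference is -7p. The variance per arm is (1-p) x 0.49 + p(1-p) x s^2, with s = 5 for daprodustat and 2 for epoetin. The lower limit is the difference minus 1.96 SE.

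| Case, per arm | Left out | Included |
|---|---|---|
| ITT 143, 12 later missing, k = 3 | 12/140: -0.89 | 15/143: -1.05 |
| ITT 143, 12 later missing, k = 1 | 12/142: -0.88 | 13/143: -0.93 |
| ITT 143, 5 later missing, k = 3 | 5/140: -0.48 | 8/143: -0.65 |
| ITT 130, 10 later missing, k = 3 | 10/127: -0.85 | 13/130: -1.02 |
| ITT 133, 10 later missing, k = 3 | 10/130: -0.83 | 13/133: -0.9995 |

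The first and fourth rows cross -1.0. The fifth, differing from the fourth by three subjects in N, just does not. With one affected subject per arm, or few later losses, nothing crosses.

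**Rough simulation** of the delta-adjusted contrast (143 per arm, SD 0.8 to 1.0; included and excluded runs used separate random draws, so the figures are indicative):

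- 5% later dropout: non-inferiority rarely tipped either way (0-12% of runs).
- 10% later dropout, k = 3, both arms shifted adversely: 18-27% of runs tipped with the exclusion, 72-77% without.
- 15% later dropout, daprodustat shifted alone: 45-48% against 73-87% at k = 3, and 37-52% against 52-60% at k = 1. At a fixed SD, the excluded runs differed from one another by about 8 to 12 points, so the k = 1 change is little more than noise.
- 20% later dropout, daprodustat shifted alone: median tipping delta from about -0.90/-0.98 to -0.65/-0.68 at k = 3.

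**The case against.** The exclusion is open and reasoned. It keeps the stress test on the subjects who produced the primary estimate, and the population statement allows exceptions, so this is not a contradiction in the plan. All of that stands. It justifies keeping a restricted version, but not making it the only one.

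The number affected is likely to be small. If 13 withdrawals per arm were spread evenly over 52 weeks, 13 x 2/52 = 0.5 would fall between Weeks 2 and 4. Nothing in the plan supports three or more per arm. This stands, and it limits the size of the point.

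A reader might infer that these are the most influential subjects throughout the grid. The limits prevent that. From 12.0 g/dL, such a subject reaches the floor at Week 40 with delta -0.5 (10 x -0.5 = -5). A subject first missing at Week 24 reaches it at Week 40 with delta -1.0 (5 x -1.0 = -5). Beyond that the two weigh the same. Extra leverage exists only at small deltas. At -0.25, the average shift over Weeks 40-52 is 11.5 x 0.25 = 2.875 g/dL, against 2.5 x 0.25 = 0.625 for a subject first missing at Week 40.

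A reader might also infer that the plan does overstate robustness, or that including these subjects would reverse the conclusion. The documents give no counts to support either. The reversals above occur at the extreme corner, and Section 7.1.6.3 questions the conclusion only if the tipping scenario is clinically plausible.

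Section 15.7.2 says subjects excluded from analyses will be documented in the study report, if applicable. That makes the exclusion visible but does not show its effect.

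**Conclusion.** The point holds as an avoidable gap of modest size. The only missing-not-at-random analysis of non-inferiority, labelled ITT, does not cover all ITT subjects, and the plan's own imputation could cover them. In the adverse direction (daprodustat down, epoetin up), inclusion moved the tipping point towards zero or left it unchanged in the simulation, so the exclusion can overstate robustness.

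The effect is bounded by about 0.035 g/dL per daprodustat subject, or about 0.05 per pair, assuming 143 per arm and a mean of 12.0 g/dL. It is negligible with one or two per arm. It could change whether the grid tips only with several per arm plus roughly 10-15% later dropout. SD, dropout and k are all assumptions, and the ITT set may be smaller than 143 per arm because Cohort 1 ESA non-users are outside it.

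**What to change.** In Section 7.1.6.3:

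- Delete the exclusion for the ITT tipping point analysis.
- Impute Weeks 4 to 52 for these subjects by arm from baseline Hgb, using the existing sequential model. Do not add a Week 2 term, because Cohort 1 has no Week 2 visit.
- Apply n times delta from Week 4.
- Report their number per arm with Table 2.22.

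The version restricted to subjects in the primary MMRM may be kept alongside. The mITT and PP repeats need no change.

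The cost is SAP wording and a re-run, with no new data. The downside is that the tipping region may look slightly less favourable.
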